7.2 Definition of Baseline, Study Visits, and Visit Windows

Baseline is defined as the last available assessment prior to first study drug dose.

For Post-Operative assessments timepoints will be assigned according to Protocol-specified visit windows. Assessment occurring 24 (\pm 2) hours from procedure completion will be assigned to the 24-hour timepoint, and so on every 24 hours, creating timepoints for 48, 72... hours.

All other analyses will use the visits and time points as reported in the eCRF. No further reassignment of the visits will be done.

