6.13 Removal of Patients from the Trial or Treatment

The investigator may withdraw a patient from the study for any of the following reasons:

- The investigator believes it is in the best interest of the patient to discontinue the study
- The Sponsor or investigator terminates the study
- The patient withdraws consent or requests to be discontinued from the study
- The patient is non-compliant

In case of early withdrawal of the patient, he will be asked to perform the 48 (\pm 4) hour visit assessment after last administration of LR769, unless he has withdrawn Informed Consent.

The investigator may discontinue a patient from LR769 treatment for any of the following reasons:

- AE or SAE possibly related to LR769 treatment
- A clinically significant change in the patient's condition that does not allow safe administration of LR769
- Per judgment of the investigator, if an adequate hemostatic response is not achieved with LR769, and the bleeding requires continued treatment, the treating physician should stop treatment with LR769 and treat the patient with a rescue therapy, such as another bypassing agent (e.g., FEIBA® or NovoSeven®) and/or other effective hemostatic treatment. The patient remains eligible for treatment with LR769 for a new surgical procedure taking into account the pharmacodynamic half-life of the rescue therapy given.

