7.5 Early Termination Procedures

- Efficacy assessment by investigator or designee
- Assessment of concomitant medications
- Postoperative assessment
- Vital signs
- Clinical safety laboratory tests (hematology, chemistry, urinalysis) by local laboratory; per weight requirement
- Assessment of AEs (including thromboembolic assessments)
- Immunogenicity sample (including storage serum sample for future use)
- Physical Examination (excluding height)

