No imputation for the end date of AEs will be done. However, the end date of concomitant medications will be imputed as the last day of the month if only the day is missing, and as December 31st of the year if both the day and the month are missing.

No other imputation of missing data will be done.

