7.7.1 Analysis of Primary Efficacy Endpoint

The primary efficacy endpoint is the percentage of surgical or other invasive procedures with a “good” or “excellent” response to LR769 treatment, as assessed by the investigator at the study center 48 (\pm 4) hours after the last administration of LR769; this assessment will be based upon the totality of assessments performed on the patient at each timepoint, also taking into consideration the surgeon’s intraoperative hemostatic assessment, the number of (interventions for) bleeding episodes, oozing, blood transfusions, and the amount of LR769 used. An additional sensitivity analysis will be performed in which patients whose 48-hour assessment is missing are treated as failures.

The proportion of “good” and “excellent” responses at 48 (\pm 4) hours will be summarized. Clopper-Pearson exact 95% confidence interval for proportion will be calculated for each surgery type and age group and overall. The summaries will include missing assessments in percent calculation, while they will still be discarded when calculating the proportion of successes and the confidence interval (CI). The missing values imputed as per section 7.3 of this SAP will be analyzed as imputed.

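### No SAP rule brings the Early Termination efficacy rating into the primary analysis, so a recorded Moderate or Poor can fall out of the headline success rate

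*SAP*

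**What the plan says.** **Collection.** Protocol 7.5 lists "Efficacy assessment by investigator or designee" among the Early Termination procedures, and Appendix 1 gives that visit its own column with an investigator's assessment. Protocol 6.13 sets a different expectation: "In case of early withdrawal of the patient, he will be asked to perform the" 48 (±4) hour assessment, unless consent has been withdrawn. Neither section refers to the other.

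**Endpoint.** The primary outcome is the investigator's rating at the study center 48 (±4) hours after the last LR769 dose. SAP 7.7.1 adds that "this assessment will be based upon the totality of assessments performed on the patient at each timepoint".

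**Timepoints.** SAP 7.2 has two rules. The first: "For Post-Operative assessments timepoints will be assigned according to Protocol-specified visit windows". Its worked example counts 24, 48, 72 hours from procedure completion. The second keeps the eCRF visits and time points for all other analyses and adds: "No further reassignment of the visits will be done". Early Termination appears in neither.

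**Missing final rating.** SAP 7.3 imputes Poor only if (1) the patient was withdrawn within 2 days of the last dose because of an adverse event or by the investigator's decision, and (2) an antihemorrhagic was used as rescue within 52 hours of the last dose. It then closes with "No other imputation of missing data will be done". Under SAP 7.7.1, missing assessments appear in the summary percentages, "while they will still be discarded when calculating the proportion of successes and the confidence interval (CI". A separate sensitivity analysis counts a missing 48-hour assessment as a failure.

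**The concern.** The trial schedules a hemostasis rating when a patient leaves early, on the same four-level scale as the primary outcome. If that rating is Moderate or Poor and no 48-hour rating follows, the database holds a recorded treatment failure that the main analysis treats as absent. That sits badly with a final assessment defined as resting on everything observed.

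When the discarded rating is a failure, the main success proportion moves upward. With a planned minimum of 12 procedures, 6 of them major, one case is visible in the headline. The sensitivity analysis ignores the rating too: it would turn a recorded Good or Excellent at Early Termination into a failure. Neither planned analysis uses what was observed.

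**Working it through.** **Plan figures.** The documents give no assumed success rate, null value, power or dropout rate, so there is no plan figure to reproduce. The inputs are the minimum of 12 procedures including 6 major ones (SAP 4) and the Clopper-Pearson 95% interval (SAP 7.7.1). The number of affected procedures is my assumption.

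**Step 1: trace a withdrawn procedure rated Moderate or Poor at Early Termination.**

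| Situation | Main analysis | Sensitivity analysis |
|---|---|---|
| 48-hour rating obtained as Protocol 6.13 asks | that rating is used | same |
| No 48-hour rating, both SAP 7.3 conditions met | imputed Poor, counted as failure | failure |
| No 48-hour rating, one or both conditions not met | discarded | failure |

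Only the third row is a problem.

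**Step 2: can the third row occur?** Yes, by either condition.
- Condition 1 fails when the patient withdraws consent, when the sponsor terminates the study, or when non-compliance is recorded as its own reason. All are withdrawal reasons in Protocol 6.13.
- Condition 2 fails when there was no antihemorrhagic rescue. In Protocol 6.8, Moderate is defined by blood loss and transfusion, not by rescue. Poor can be reached through transfusion, hypotension or unexpected ICU transfer without rescue.

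**Step 3: size.** With x successes in n procedures, the Clopper-Pearson lower limit is the 0.025 quantile of Beta(x, n−x+1), and the upper limit is the 0.975 quantile of Beta(x+1, n−x), or 1 when x = n. When x = n the lower limit reduces to 0.025^(1/n): 0.025^(1/11) = 0.715 and 0.025^(1/12) = 0.735.

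All other procedures are assumed successful, except in the row that says otherwise:

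| Scenario | Early Termination failure discarded | Early Termination failure counted |
|---|---|---|
| 12 procedures, 1 case | 11/11 = 100% (71.5–100) | 11/12 = 91.7% (61.5–99.8) |
| 12 procedures, 2 cases | 10/10 = 100% (69.2–100) | 10/12 = 83.3% (51.6–97.9) |
| 12 procedures, 1 case plus 1 other observed failure | 10/11 = 90.9% (58.7–99.8) | 10/12 = 83.3% (51.6–97.9) |
| 6 major procedures, 1 case | 5/5 = 100% (47.8–100) | 5/6 = 83.3% (35.9–99.6) |
| 12 plus a successful replacement, 1 case | 12/12 = 100% (73.5–100) | 12/13 = 92.3% (64.0–99.8) |
| 6 major plus a successful replacement, 1 case | 6/6 = 100% (54.1–100) | 6/7 = 85.7% (42.1–99.6) |

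The replacement rows apply if Protocol 6.14 is triggered, that is, if removal leaves the minimum unmet.

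**Step 4: compare with the sensitivity analysis.** For a Moderate or Poor at Early Termination, missing-as-failure gives the right-hand column exactly. For one procedure rated Good or Excellent at Early Termination, the main analysis gives 11/11 (71.5–100), the sensitivity analysis 11/12 (61.5–99.8), and using the rating 12/12 (73.5–100).

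**The case against.** The strongest reply is that the plan already contains the damage, and most of its parts stand.

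- Protocol 6.13 asks withdrawn patients for the 48-hour assessment. It also lists inadequate hemostasis under stopping LR769, not under leaving the study, so a treatment failure can still be rated at 48 hours. This makes the affected group small. It does not empty it, because the visit is a request and withdrawn consent is exempt. A patient who withdraws consent may also never be rated at Early Termination.
- SAP 7.3 keeps some withdrawn failures in the denominator as Poor. A reader might infer that every withdrawn procedure rated Moderate or Poor is dropped. The documents do not support that.
- The sensitivity analysis reports the lower figure, missing assessments are shown in the summary percentages, and post-operative ratings are listed (SAP 7.7.2). The case would be visible, though not in the headline estimate.
- No success threshold or hypothesis test is attached to the primary endpoint, so no stated decision turns on the difference.

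A reader might also infer that SAP 7.2 forbids using an Early Termination rating made 44–52 hours after the last dose. The text does not establish this. The bar on reassignment follows the sentence about all other analyses, while post-operative ratings fall under the preceding window rule, and 48 (±4) hours after the last dose is a protocol window. Against that, the worked example counts only from procedure completion. The eCRF label for such a rating is also unknown: the SAP change log says only that post-operative assessments share one generic 24-hourly label. The rule is ambiguous.

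Finally, an Early Termination rating is not the same measurement as the 48-hour rating. It may come earlier, and a designee may make it. That argues for flagging it, and against a rule that uses only unfavorable early ratings. Counting early Moderate or Poor as failure while setting early Good or Excellent to missing would bias the estimate downward.

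**Conclusion.** The concern holds in a limited form. The stated rules give the Early Termination rating no explicit path into the main primary analysis. A recorded Moderate or Poor is discarded when there is no 48-hour rating and the two SAP 7.3 conditions are not both met.

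With one such case and all else successful, the point estimate is overstated by 8.3 percentage points at the 12-procedure minimum (100% − 91.7%), or by 7.7 points with a successful replacement (100% − 92.3%). In a major stratum of 6, without replacement, the gap is 16.7 points (100% − 83.3%).

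These sizes rest on an assumed count of one. The documents give no dropout figure, and the group is narrow. It is also not shown that withdrawn procedures are mostly failures, so no general upward bias can be claimed. The defect concerns the headline figure and its interval, since the sensitivity analysis already reports the lower value. It is worth correcting because a recorded outcome should not depend on a gap in the rules.

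**What to change.** - **SAP 7.3 and 7.7.1:** when the 48-hour rating is absent and the Poor imputation does not apply, use the recorded Early Termination rating in the main analysis in both directions: Moderate or Poor as failure, Good or Excellent as success. Flag any rating made outside 44–52 hours after the last dose.
- **SAP 7.7.1:** keep missing-as-failure as the conservative sensitivity analysis. Apply it to every procedure without a rating from the 48-hour visit itself, including those filled from Early Termination.
- **SAP 7.2:** state that an Early Termination rating made 44–52 hours after the last dose is the 48-hour assessment.
- **Protocol 7.5 and 6.13:** reconcile the two accounts of what a withdrawn patient undergoes, including who makes the rating. The primary endpoint specifies the investigator; 7.5 allows a designee.

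The cost is SAP wording plus a protocol clarification, since the data are already scheduled for collection. SAP 7.1 allows the methods to be updated before database lock, but asks for a protocol amendment if the change may affect the primary conclusions. The downsides are that an earlier rating only approximates the 48-hour totality rating, and that the estimate may come out slightly less favorable.

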7.3 Handling of Missing Data

Any imputation of missing or incomplete data will be flagged in the analysis datasets. The original value will be kept for traceability.

Missing Final Assessment of Postoperative Response (48 [\pm 4] hours after the last dose of LR769)

In accordance with the definition of postoperative assessment in section 6.8 of the Protocol, missing final postoperative assessment of treatment response by the investigator will be imputed to "Poor", if and only if, both of the following conditions are satisfied: (1) patient was withdrawn from study, within 2 days after the last dose of LR769, due to adverse event or by Investigator's decision and (2) rescue therapy (any medication in antihemorrhagics ATC subgroup) was used within 52 hours after the last dose of LR769.

Incomplete/Missing Dates

Dates of historical events such as the date of diagnosis, date of onset, start/stop dates of previous treatment, start dates of medical conditions, etc. will be imputed when partial dates are collected. In case of missing month and day and available year YYYY the corresponding date will be replaced with "01JULYYYY". In case of missing day the date will be replaced with "15MMMYYYY".

The following rules will be applied for AEs and concomitant medications with incomplete dates:

- If Day is missing for Start Date and Month and Year are the same as Month and Year for the First Treatment Date, then Start Date equals First Treatment Date.
- If Day is missing for Start Date and Month and Year are not the same as Month and Year for the First Treatment Date, then impute Day 1 of the month.
- If Day and Month are missing for Start Date and the Year is the same as the Year for the First Treatment Date, then Start Date equals First Treatment Date.
- If Day and Month are missing for Start Date and the Year is not the same as the Year for the First Treatment Date, then impute July 1st of the year.

- If the Start Date is missing entirely, impute the start date with minimum between the End date of AE and First Treatment Date. Therefore, if an AE with missing start date has ended before the start of the treatment, the Start Date will be imputed with the End Date, and if the AE in question ended after the First Treatment Date, then the Start Date will be imputed with the First Treatment Date.

No imputation for the end date of AEs will be done. However, the end date of concomitant medications will be imputed as the last day of the month if only the day is missing, and as December 31st of the year if both the day and the month are missing.

No other imputation of missing data will be done.

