5.6 Restrictions

5.6.1 Prohibited Medications

All aspirin, NSAIDs, herbs, natural medications, or any other drug with platelet inhibitory properties must be discontinued at least 1 week prior to elective surgical or other invasive procedure and for the duration of treatment with LR769.

Additional restrictions to concomitant therapies include the use of other sources of FVIIa, such as aPCC (FEIBA[®]) or NovoSeven[®]. These products may be used only if the response to LR769 is considered insufficient (ie, treatment failure), in which case these bypassing agents may be used for rescue therapy.

Other agents for the prevention of excessive bleeding during surgical or other invasive procedures, such as antifibrinolytics, are allowed and will be recorded on the eCRF.

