- Moderate: postoperative blood loss that is substantially greater than expected following this type of procedure in a patient who does not have a bleeding disorder and who is undergoing the same surgical or other invasive procedure, not explained by a surgical/medical issue other than hemophilia; additional blood component [within 2-fold greater than expected] transfusion is necessary
- Poor: uncontrolled postoperative blood loss, not explained by a surgical/medical issue other than hemophilia that requires intervention (rescue therapy requirement [bypass agent or porcine FVIII], and/or increased blood component [>2 -fold greater than expected] transfusion, and/or leads to hypotension or unexpected transfer to Intensive Care Unit [ICU])

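### SAP 7.3 imputes Poor for a rescued procedure with no 48-hour rating only if the patient also left the study for a named reason, so some rescued procedures drop out of the primary proportion

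*SAP*

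**What the plan says.** SAP 7.3 imputes a missing final rating to Poor "if and only if, both of the following conditions are satisfied: (1) patient was withdrawn from study" within 2 days of the last LR769 dose, because of an adverse event or by the investigator's decision, and (2) "rescue therapy (any medication in antihemorrhagics ATC subgroup) was used within 52 hours after the last dose of LR769". It presents this as following protocol 6.8 and allows no other imputation of the rating. SAP 7.7.1 discards the remaining missing ratings from the success proportion and its Clopper-Pearson interval. It keeps them in the summary percentages and adds a sensitivity analysis in which a missing 48-hour rating is a failure.

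Protocol 6.8 defines postoperative Poor as "uncontrolled postoperative blood loss, not explained by a surgical/medical issue other than hemophilia that requires intervention". Rescue with a bypass agent or porcine FVIII is one such intervention. Protocol 5.6.1 says of other FVIIa sources: "These products may be used only if the response to LR769 is considered insufficient (ie, treatment failure"). It also says: "Other agents for the prevention of excessive bleeding during surgical or other invasive procedures, such as antifibrinolytics, are allowed".

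Protocol 6.13 has two lists. One gives reasons for withdrawing a patient from the study. The other begins "The investigator may discontinue a patient from LR769 treatment for any of the following reasons", and rescue for inadequate hemostasis is in that second list. Patients withdrawn early are asked to attend the 48-hour "visit assessment after last administration of LR769, unless he has withdrawn Informed Consent".

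**The concern.** The primary endpoint is a single proportion, from as few as 12 procedures, with no control arm. Rescue after an insufficient response is close to what the protocol means by failure. Whether such a procedure counts should not depend on how the patient's later participation ended.

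Condition (1) makes it depend on that. It covers patients withdrawn for an adverse event or by the investigator, who are still asked to attend the 48-hour visit. It does not cover patients who withdrew consent, the one group for whom the visit is waived. For rescued procedures the omission can only raise the reported success rate.

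**Working it through.** **Step 1: which rescued, unrated procedures are dropped.** The Efficacy Population needs only one efficacy assessment, so a procedure with an intraoperative rating stays in the population. Its place in the primary proportion then depends on SAP 7.3.

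| Rescued, 48 h rating missing, and the patient | Result under SAP 7.3 and 7.7.1 |
|---|---|
| was withdrawn within 2 days for an AE or by investigator decision | imputed Poor |
| withdrew consent | dropped |
| stayed in the study but missed the visit | dropped |
| left through sponsor termination | not named in condition (1) |
| was withdrawn for non-compliance | unclear: may count as investigator decision |
| was withdrawn for an AE at 48 to 52 h | dropped only if 2 days means 48 h |

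The last row arises because condition (2) and the visit window both run to 48 + 4 = 52 h, while condition (1) stops at 2 days.

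**Step 2: size.** The plan gives no figure to reproduce: no target rate, power or expected number of missing ratings. The protocol minimums are 12 procedures, 6 of them major. The numbers of rescued, unrated procedures (k) and rated failures (f), and a larger study of N = 20, are assumptions.

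- Counted as failures: (N − k − f)/N. Reported under the SAP: (N − k − f)/(N − k).
- Clopper-Pearson 95% limits for x of n: lower = 0.025 quantile of Beta(x, n − x + 1); upper = 0.975 quantile of Beta(x + 1, n − x). When x = n, the lower limit is 0.025^(1/n) and the upper is 1. For example, 0.025^(1/11) = 0.715.

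| N, k, f | Counted as failure | Reported under the SAP |
|---|---|---|
| 12, 0, 0 | 12/12 = 100% (73.5 to 100) | the same |
| 12, 1, 0 | 11/12 = 91.7% (61.5 to 99.8) | 11/11 = 100% (71.5 to 100) |
| 12, 1, 1 | 10/12 = 83.3% (51.6 to 97.9) | 10/11 = 90.9% (58.7 to 99.8) |
| 12, 2, 0 | 10/12 = 83.3% (51.6 to 97.9) | 10/10 = 100% (69.2 to 100) |
| 20, 1, 0 | 19/20 = 95.0% (75.1 to 99.9) | 19/19 = 100% (82.4 to 100) |
| 6 major, 1, 0 | 5/6 = 83.3% (35.9 to 99.6) | 5/5 = 100% (47.8 to 100) |

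One case among 12 moves the estimate by 100 − 91.7 = 8.3 points and the lower limit by 71.5 − 61.5 = 10.0 points.

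**Step 3: the rescue definition.** SAP 7.3 uses an ATC subgroup. Protocol 6.8 names a bypass agent or porcine FVIII. Protocol 6.13 adds "and/or other effective hemostatic treatment". The documents do not list the members of the ATC subgroup. If it includes antifibrinolytics (an assumption), deleting condition (1) alone would create the opposite error. With 12 procedures and no failure, one unrated patient who did well on a permitted antifibrinolytic would turn 11/11 = 100% (71.5 to 100) into 11/12 = 91.7% (61.5 to 99.8).

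**The case against.** The strongest reply is that the alternative figure is already planned. When the rescued procedure is the only missing rating, the missing-as-failure analysis gives exactly the figure in the middle column of the second table. Missing ratings also stay in the summary percentages, and response assessments and concomitant medications are listed. Efficacy is descriptive, with no success threshold. This stands as a limit on the harm. It does not make the main estimate right, and the sensitivity analysis cannot separate a rescued patient from one who did well and missed the visit. With one of each among 12 and ten rated successes, the main analysis gives 10/10 = 100%, counting only the rescued case as a failure gives 10/11 = 90.9%, and missing-as-failure gives 10/12 = 83.3%.

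A second reply is that the gap is narrow. It needs rescue, a missing rating and an uncovered reason together, and a rescued patient who stays in the study is still due the visit. This also stands.

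A third is that condition (1) guards against false failures under a broad ATC definition. That is a fair reason not to delete it in isolation. A narrower definition of rescue does the same job without discarding rescued cases.

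A reader might also infer that non-compliance withdrawals are certainly dropped. The documents do not establish this: protocol 6.13 lists non-compliance among reasons for which the investigator may withdraw a patient, and the eCRF disposition categories are not given.

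**Conclusion.** The point holds in limited form. As written, SAP 7.3 and 7.7.1 remove a rescued, unrated procedure from the primary proportion and interval when the patient withdrew consent or missed the visit while still in the study. Those two routes are secure. Sponsor termination is not named in condition (1), non-compliance is unclear, and the mismatch in time limits matters only if 2 days means 48 h.

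The effect is zero if no such case occurs. One case with no other failure turns 91.7% into 100% at 12 procedures, and 83.3% into 100% at 6 major procedures. These counts are assumptions.

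Two stronger readings are tempting. One is that every dropped case is a documented treatment failure. Protocol 5.6.1 applies that label to use of other FVIIa sources after insufficient response, and protocol 6.8 requires uncontrolled bleeding not otherwise explained, so rescue alone does not settle each case. The other is that the trial's conclusion would change. With no threshold and a planned sensitivity analysis, the documents do not support that. The defect is in the headline estimate, and it is cheap to correct.

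**What to change.** In SAP 7.3, make these changes in one edit:

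- Delete condition (1). Impute Poor for any procedure with no 48-hour rating in which rescue was recorded within the existing 52-hour window, whatever the withdrawal status or reason. Exempt cases where the record already gives a surgical or medical explanation other than hemophilia.
- Replace the ATC subgroup with the agents protocol 6.8 names (bypass agent or porcine FVIII). Reconcile the rescue wording across SAP 7.3, protocol 6.8 and protocol 6.13, so that antifibrinolytics allowed for prevention are not counted as rescue by drug code alone.
- State whether the early-termination efficacy rating (protocol 7.5) has a role when the 48-hour rating is missing. If it does, use it in both directions: Poor or Moderate as failure, Good or Excellent as success. Using only Poor could only lower the rate.
- Keep the missing-as-failure sensitivity analysis.

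The cost is one SAP paragraph. Protocol 6.11 already records product, date and time, so the rule can be programmed apart from the stated exemption. The headline rate may be slightly lower. SAP 7.1 allows updates before database lock, but may require a protocol amendment if the change could affect the primary conclusions.

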7. ANALYTICAL PLAN AND STATISTICAL METHODS

7.1 General Conventions and Statistical Considerations

All statistical analyses will be performed and data appendices will be created using the SAS system version 9.4 or higher.

Data collected in this study will be presented in summary tables and patient data listings. Summary descriptive statistics for continuous variables will include the number of observations with non missing values, number of observations with missing values, mean, standard deviation (SD), median, and minimum and maximum values. All raw data will be presented to the original number of decimal places. Means, medians, quartile 1 (Q1), and quartile 3 (Q3) will be presented to 1 more decimal place than in the raw data. Standard deviations will be presented to 2 more decimal places than in the raw data. All data collected will be presented in the data listings.

Summary tables for categorical variables will include the number and percentage of observations for each category. If not specified additionally, the number of observations with non missing values will be the denominator for percentage calculation.

Unless otherwise stated, all statistical tests will be performed using 2-sided tests at the 5% significance level. P-values less than 0.001 will be displayed as <0.001 in the outputs.

Analyses will be stratified by the type of surgery (Minor/Major).

The protocol allows for one patient to enter the study more than one time (for different procedures). Baseline characteristics and demography data will be summarized on a patient level, while efficacy and safety assessments are to be analyzed on a procedure level. Procedure characteristics and disposition will also be summarized on a procedure level. When performing analysis on a patient level, the first value observed for a patient is to be reported (for instance, age that was recorded during the first procedure for the patient will be summarized in the demographics). All tables will contain explicit footnotes to describe on what level the data are summarized.

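### SAP 7.3: the partial start-date rules ignore a known end date, so an AE or drug that ended before dosing can be given a start on the first treatment date

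*SAP*

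**What the plan says.** SAP 7.3 lists five start-date rules, introduced by "The following rules will be applied for AEs and concomitant medications with incomplete dates". Numbered in the order given:

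1. Day missing, month and year matching first treatment. The rule opens "If Day is missing for Start Date and Month and Year are the same as Month and Year for the First Treatment Date" and sets the start to the First Treatment Date.
2. Day missing, different month or year: the start is day 1 of the recorded month.
3. Day and month missing, same year. The rule opens "If Day and Month are missing for Start Date and the Year is the same as the Year for the First Treatment Date" and again uses the First Treatment Date.
4. Day and month missing, different year: "then impute July 1st of the year".
5. Nothing known: "If the Start Date is missing entirely, impute the start date with minimum between the End date of AE and First Treatment Date". The SAP spells out the purpose: "if an AE with missing start date has ended before the start of the treatment, the Start Date will be imputed with the End Date".

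Imputations are flagged and the recorded values kept. AE end dates are never imputed. SAP 7.8.2 classes an AE as treatment-emergent if it occurred or worsened after the first dose. SAP 7.9.2 classes a drug as concomitant if it started in the treatment period, or started earlier and ended within it.

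On re-entry, SAP 7.1 notes that "The protocol allows for one patient to enter the study more than one time" and analyses efficacy and safety per procedure. SAP 7.2 says "Baseline is defined as the last available assessment prior to first study drug dose". Neither that definition nor First Treatment Date in 7.3 is tied to a particular procedure.

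**The concern.** Rule 5 protects a record that ended before dosing; rules 1 and 3 do not. Knowing the month or year of onset therefore gives a worse date than knowing nothing. The imputed start can fall after the record's own end, which is impossible, and it falls on the date that separates pre-treatment from on-treatment.

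Such records can arise by design. AEs are collected from consent (Protocol 6.9.2), screening runs from Day -21 to Day -1 (Protocol 7.1), and medications are recorded from 30 days before screening (Protocol 5.5). At stake is the TEAE or concomitant status of individual records. In a study whose minimum is 12 procedures in 6 patients, one misplaced event is visible in a safety table.

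**Working it through.** The documents give no figure to reproduce, so the check applies the five rules literally. The dates below are illustrative, not trial data.

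**Worked case.** First dose 20 March 2017; AE end recorded as 10 March 2017.

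| Recorded start | Rule | Imputed start | After own end? |
|---|---|---|---|
| March 2017, no day | 1 | 20 March | Yes, by 20 − 10 = 10 days |
| 2017 only | 3 | 20 March | Yes, by 10 days |
| Nothing | 5 | min(10 March, 20 March) = 10 March | No |

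**How often a pre-dose date pattern is caught.** Take every first-dose date in 2017 (365) and every onset and end lying wholly in Days -21 to -1.

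- An onset k days before dosing has k possible end days, so there are 1 + 2 + … + 21 = 231 pairs per dose date, and 365 × 231 = 84,315 in all.
- An onset k days before dosing falls in the previous month only when dosing is on days 1 to k of a month. Pairs that cross one month boundary number Σk² for k = 1 to 21, which is 21 × 22 × 43 / 6 = 3,311.
- Day missing: 12 boundaries give 12 × 3,311 = 39,732 crossings. The other 84,315 − 39,732 = 44,583 (52.9%) are moved to the first-dose date.
- Day and month missing: only the year boundary helps, so 84,315 − 3,311 = 81,004 (96.1%) are moved.
- Start wholly missing: 0 are moved.
- With the imputed start capped at the recorded end date: 0 of 84,315 under each pattern.

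**Rules 2 and 4.** Rule 2 uses the first of the recorded month, so it cannot pass an end date in that month or later. Rule 4 can: first dose 20 December 2016, AE start recorded as 2017 and end 10 January 2017 gives 1 July 2017. Status is still right, because a later-year start stays after first dose and an earlier-year start stays before it.

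**Re-entry.** Suppose first doses on 5 February and 10 June 2017.

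- AE start known only as 2017, end 15 June: the imputed start is 5 February if First Treatment Date is per patient, and 10 June if it is per procedure. The event changes procedure.
- AE start June 2017 with no day, end 8 June: a per-patient date gives 1 June (rule 2). A per-procedure date gives 10 June (rule 1), after the AE ended. Defining the date per procedure therefore does not remove the need for the cap.

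**The case against.** The best defence is that this is a drafting gap with almost no practical reach. Start date and time are required for AEs (Protocol 6.9.1) and recorded for medications (Protocol 5.5 and 6.11), eCRF data are fully source-verified (Protocol 10.6), and discrepancies are queried (Protocol 10.7). Partial dates should be few. Moving an uncertain onset to first dose is also a deliberately cautious convention, and the safety analysis is descriptive because SAP 9 drops the paired t-tests. All of this stands and limits the severity. It does not justify a start date later than a known end, where onset before dosing is no longer uncertain.

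Several stronger readings are tempting, but the documents do not support them:

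- *The SAP never checks the end date.* Rule 5 does, and it handles AEs correctly. What is unclear there is medications, since it names only the AE end date.
- *The July 1 rule misclassifies events.* It can give an implausible date but, as shown, not a wrong status relative to first dose.
- *The primary endpoint is affected through the rescue condition.* Imputing the final response as poor needs a missing final assessment, a qualifying withdrawal within 2 days of the last dose, and an antihemorrhagic used within 52 hours after that dose. A drug whose recorded end precedes the first dose was not used then.
- *A second procedure takes its baseline from the first.* The term is undefined, not fixed. SAP 7.1 reserves the first observed value for patient-level analyses, the change log speaks of multiple enrollment, and SAP 7.4 counts prior PERSEPT 3 enrollment. A per-entry reading is open.

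**Conclusion.** The point holds as a minor defect. Rules 1 and 3 in SAP 7.3 can place a start after a known pre-dose end, on the First Treatment Date. Counting such a record as a TEAE assumes that a start on the first-dose date is treated as after dosing, which the SAP does not settle. Counting the drug as started on treatment assumes that the treatment period includes that date.

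The 52.9% and 96.1% are shares of possible date patterns under an even spread, given a partial start and a complete pre-dose end. They are not expected error rates, and the number of such records is unknown. A simpler figure, the mean of (30 − k)/30 for k = 1 to 21, or 19/30 = 63%, is only the share of onsets in the same 30-day month as dosing, whatever their end date.

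The undefined First Treatment Date is a separate ambiguity. It mainly affects which procedure an event belongs to. At exactly 12 procedures in 6 patients, 12 − 6 = 6 would be repeats, but both numbers are minima, so this is neither a forecast nor a bound.

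**What to change.** In SAP 7.3 add: *An imputed start date is never later than a known recorded end date (AE or medication); if it would be, use the end date.* Extend the wholly-missing rule to the medication end date. Records with no end date, or one after dosing, are unaffected.

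As a secondary clarification, state in SAP 7.2 and 7.3 that baseline and First Treatment Date refer to the first LR769 dose of the procedure concerned. A partly dated record has to be linked to a procedure before its date can be imputed, so say how. The study entry under which it was collected would serve, assuming the eCRF keeps entries separate.

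Leave the TEAE definition in SAP 7.8.2 unchanged. Tying it to each procedure's first dose would make AEs that arise between procedures, in patients already exposed, non-treatment-emergent. That would contradict Protocol 6.9.9 and the SAP's own assignment of a TEAE to the latest prior procedure.

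The cost is a few sentences and minor programming. SAP 7.1 allows such updates before database lock.
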